# Table 8.1. Noncompartmental Pharmacokinetic Parameters to be Calculated

Parameter	Label to be Used in the Text, Tables and Figures	Definition	Method of Determination
AUC %extrap	AUC%extrap	Percent of AUC inf extrapolated to infinity	Calculated as: (1 – AUCt/AUCinf) x 100
C max	Cmax	Maximum baseline-adjusted plasma concentration over the duration of the measurement interval.	Taken from bioanalytical data adjusted for baseline
C last	Clast	Plasma baseline-adjusted nicotine concentration at last time point measured.	Taken from bioanalytical data adjusted for baseline
T max	T max	Time to reach the maximum baseline-adjusted plasma concentration. If the maximum value occurs at more than one time point, $T_{max}$ is defined as the first time point with this value	Taken from clinical database as the difference in the time of administration and the time of the blood draw which is associated with the $C_{max}$
T  / 2	T  / 2	Apparent first-order terminal elimination half-life.	Calculated as ln2/K el
K el	Kel	Apparent first-order terminal elimination rate constant	Calculated by linear least-squares regression analysis using the maximum number of points in the terminal log-linear period (e.g., three or more non-zero plasma concentrations).

Pharmacokinetic parameters will not be calculated for subjects with less than 3 consecutive post-product administration time points with quantifiable concentrations. Subjects for whom there are insufficient data to calculate the PK parameters will be included in the concentration tables only and excluded from the summary statistics, statistical analysis, and mean profiles.

The Kel will be determined using linear regressions composed of least 3 data points. The Kel will not be calculated if 1) the terminal elimination phase is not apparent, 2) if Cmax is one of the 3 last data points, or 3) if the R^2 value is less than 0.75. In cases where the Kel interval is not calculated, the values of T/2, AUCinf, and AUC%extrap will not be reported.

# 8.5 Data Summarization and Presentation

SAS® software (Version 9.4 or higher) will be used for all data presentation and summarization including statistical analyses, summary tables, graphs, and data listings. Descriptive statistics will be generated for plasma concentrations and PK parameters.

The plasma nicotine concentrations will be listed for all subjects and presented with the same level of precision as received from the bioanalytical laboratory. Plasma nicotine concentrations will be summarised by study product and time point for all subjects in the outcomes population, by sex and overall using descriptive statistics. Summary statistics, including sample size (n), arithmetic mean (mean), standard deviation (SD), coefficient of variation (CV%), standard error of the mean (SEM), minimum, median, and maximum will be calculated for all nominal time point for both baseline-adjusted and unadjusted concentrations. Excluded subjects or timepoints will be included in the concentration tables, but will be excluded from the summary statistics and noted as such in the tables. All BLQ values will be presented as "BLQ" in the concentration tables and footnoted accordingly.

Mean and individual concentration-time profiles will be presented on linear and semi-log scales. Linear mean plots will be presented with and without SD.

Plasma nicotine PK parameters will be listed and summarised by product (overall and by sex) for all subjects in the Outcomes Population. Pharmacokinetic parameters will be reported to 3 significant figures for individual parameters, with the exception of  $T_{max}$ , which will be presented with 2 decimal places. Summary statistics will be reported, including n, mean, SD, CV%, SEM, minimum, median, and maximum by study product (overall and by sex). In addition, geometric mean (geom mean) and geometric CV% (geom CV%) will be provided for the Cmax and AUCt parameters by study product (overall and by sex).

Excluded subjects or any PK parameter data, as applicable, will be listed in the PK parameter tables, but will be excluded from the summary statistics and noted as such in the tables.

The level of precision for each concentration and PK parameter statistic will be presented as follows: minimum/maximum in same precision as in the bioanalytical data (concentrations) or as mentioned above for the PK parameters, mean/median/geom mean in one more level of precision than minimum/maximum, SD/SEM in one more level of precision than mean/median, n will be presented as an integer, CV% and geom CV% will be presented to the nearest tenth.

Missing data will be treated as missing and no data imputation will be conducted.

# 8.6 Statistical Analysis of Pharmacokinetic Parameters

A linear mixed model for analysis of variance (ANOVA) will be performed on the natural log-transformed PK parameters Cmax and AUCt following the controlled (morning) product use session on each of Days/Periods 1, 2, 3, 4, and 5. The model will include sequence, product, and study period as fixed effects and subject-nested-within-sequence as a random

effect. Sequence will be tested using subject-nested-within-sequence as the error term for informational purposes. Geometric least-squares means (LSM) and 95% confidence intervals (CIs) will be provided for the PK parameters of  $C_{max}$  and AUCt by study product. Geometric LSM ratio, 95% CIs of geometric LSM ratio, and p-values will be provided for the study product comparisons in  $C_{max}$  and AUCt. The comparisons of interest will include each product compared to every other product (pairwise comparisons).

The above statistical analyses will be performed using the following SAS® code:

```
Proc mixed data=<>;
class subject sequence period product;
model \log(\text{parameter}) = \text{sequence period product / ddfm}=KR;
random subject (sequence);
lsmeans product/cl alpha=0.05;
estimate "Product A versus Product E" Product 1 0 0 0 -1/cl alpha=0.05;
estimate "Product B versus Product E" Product 0 1 0 0 -1/cl alpha=0.05;
estimate "Product C versus Product E" Product 0 0 1 0 -1/cl alpha=0.05;
estimate "Product D versus Product E" Product 0 0 0 1 -1/cl alpha=0.05;
estimate "Product A versus Product D" Product 1 0 0 -1 0/cl alpha=0.05;
estimate "Product B versus Product D" Product 0 1 0 -1 0/cl alpha=0.05;
estimate "Product C versus Product D" Product 0 0 1 -1 0/cl alpha=0.05;
estimate "Product A versus Product C" Product 1 0 -1 0 0/cl alpha=0.05;
estimate "Product B versus Product C" Product 0 1 -1 0 0/cl alpha=0.05;
estimate "Product A versus Product B" Product 1 -1 0 0 0/cl alpha=0.05;
run;
```

# *Note: Protocol defined the study as Days 1-5 and the CRF had periods 1-5 (each have one day), respectively. Period will be used in the database and therefore in the statistical analysis.*

Geometric LSMs will be presented in one more precision level than the associated PK parameter. GMRs and 95% CIs will be presented with 2 decimal places and intra-subject CV% will be presented to 2 decimal places.

Non-parametric analysis of  $T_{max}$  will be performed. The nonparametric Wilcoxon Signed Rank Test will be performed and the p-value will be presented for the same comparisons calculated in the ANOVA model above.

The Hodges-Lehmann estimate for the median of the differences in  $T_{max}$ , and the 95% CI will be presented for the comparisons. The Hodges-Lehmann estimator is given by the median of all possible pairwise averages (Walsh averages) of the differences in  $T_{max}$ . The CI will be constructed using Walsh averages and the appropriate quantile of the Wilcoxon Signed Rank Test Statistic. Note that  $T_{max}$  will not be ln-transformed for these analyses.

# 8.7 Preliminary Data and Interim Analysis

Celerion Biometrics will not perform preliminary or interim analyses.

## 9. SUBJECTIVE EFFECTS ASSESSMENTS

#### 9.1 Urge to Smoke (UTS)

The Urge to Smoke (visual analogue scale (VAS)) questionnaire will be completed at Time 0 (pre-product use) and at 4, 8, 15, 45, 60, 120, and 240 minutes relative to the start of controlled product use on Days 1, 2, 3, 4, and 5.

Ratings of the subjects' 'Right now, how much would you like to smoke a cigarette?' recorded on a 100 mm VAS scale ranging from "Not at all" (0) to "A great deal" (100) will be reported.

The following parameters will be calculated for the urge to smoke assessments:

Emax	The maximum change from baseline VAS score (VAS $_{preuse}$ - VAS $_{postuse}$ ).
TE max	Time of the $E_{max}$ . If the maximum value occurs at more than one time point, $TE_{max}$ will be defined as the first time point with this value.
AUEC 0-240	The area under the change from baseline VAS score versus time curve from time 0 to 240 minutes.

Baseline (VASpreuse) will be the VAS result closest and prior to product use for the respective product. Responses, change from baseline, and derived parameters will be listed by subject and summarised by product, by sex and overall using descriptive statistics (n, mean, SD, CV%, SEM, minimum, Q1, median, Q3, maximum, and 95% CI.)

A linear mixed model for ANOVA will be performed on the urge to smoke parameters (no data transformation). The model will include sequence, product, and study period as fixed effects and subject-nested-within-sequence as a random effect. Sequence will be tested using subject-nested-within-sequence as the error term for informational purposes. LSMs and 95% CIs will be provided for Emax and AUCEC0-240 by study product. LSM differences, 95% CIs of LSM differences, and p-values will be provided for the study product comparisons in Emax and AUCEC0-240. The same comparisons from PK analysis detailed above will be used.

The ANOVA analysis will be performed using the same SAS® code as outlined in the Statistical Analysis of Pharmacokinetic Parameters section above.

# 9.2 Product Evaluation Scale (PES)

The Product Evaluation Scale questionnaire will be completed at 240 minutes for each product use on Days 1, 2, 3, 4, and 5.

Product Evaluation will be considered as a 7-point scale (1 = not at all, 2 = very little, 3 = a little, 4 = moderately, 5 = a lot, 6 = quite a lot, and 7 = extremely). Responses will be presented as the following factor scores:

a) Satisfaction: average of the response scores from questions 1, 2, 3, and 12;

- b) Psychological reward: average of the response scores from questions 4 to 8;
- c) Aversion: average of the response scores from questions 9, 10, 16, and 18;
- d) Relief: average of items 11, 13, 14, 15, and reversed for item 20 (i.e., not at all = 7, extremely = 1);
- e) Items 17, 19, 21 will be summarised as individual item scores.

Descriptive statistics of the subscales will be provided by study product, by sex and overall. Individual responses will be listed by subject.

# 9.3 Intent to Use (ITU)

The Intent to Use (VAS) questionnaire will be completed at 240 minutes for each product use on Days 1, 2, 3, 4, and 5.

Ratings of the subjects' 'If available, how likely are you to buy your assigned study product in the future?' recorded on a 100 mm VAS scale ranging from "Not at all" (0) to "Extremely" (100) will be reported.

In addition, responses to the ITU questionnaire will also be treated as a bipolar variable. The bipolar score will be calculated by subtracting 50 from the original VAS score, then categorizing into three categories: -50 to < 0, 0, and > 0 to 50.

Descriptive statistics of the VAS raw score and bipolar score will be provided by study product. Individual responses will be listed by subject. A frequency count table will be presented for the categories of the bipolar scores.

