1.3 Study Purpose

This study is being conducted to evaluate the overall performance of [REDACTED] heating device when used with [REDACTED] HTP consumables (stick HHP consumables compared with CC). The study will provide data on nicotine PK, product perception and preference, product usage as measured by topography and tolerability and safety of each of the products compared with subjects' own brand combustible cigarettes (OBCC). The results of this study are intended to contribute to an awareness of the harm reduction potential of the [REDACTED] device when used with i [REDACTED] (ITP) and [REDACTED] (IHP) sticks, and the data may be included in future premarket tobacco application submissions to the Food and Drug Administration Center for Tobacco Products in the United States based on Section 910 of the Federal Food, Drug, and Cosmetic Act - Application for Review of Certain Tobacco Products (FDA 2019).

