7.3.2.3 Intent to Use

Descriptive statistics of the VAS will be provided by study product. Individual responses will be listed by subject.

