#### Secondary

- 1. To evaluate other pharmacokinetic (PK) parameters of nicotine after the controlled use of each HTP, HHP, or cigarette comparator.
- 2. To evaluate the change in smoking urges observed after the controlled use of each HTP, HHP, or cigarette comparator.
- 3. To evaluate product perception and preference using subjective assessments.
- 4. To evaluate the tolerability and safety of each of the products used.
- 5. To investigate usage behaviour for each product using measurements of topography parameters (puff count, puff duration, puff volume, peak puff flow rate, average puff flow rate, inter puff interval) for each product following *ad libitum* product use sessions.

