## Table SCUTS Statistical Comparison of Urge to Smoke VAS Parameters Emax and AUECO-240 Following Controlled Product Use (Outcomes Population)

Programmer note: The table should include all the comparisons of interest listed in Section 8.6.

Product A: < > Product B: < > Product C: < > Product D: < > Product E: < > Test = The first

Test = The first product in the comparison; Reference = The second product in the comparison; n = Number of observations used in analysis The mixed model includes sequence, product, and study period as fixed effects and subject-nested-within-sequence as a random effect. Mixed model with a default (variance component) covariance structure was used. Least-squares means (LS Means) are calculated from the ANOVA.

Source: ADaM.< >

Program: /CAXXXX/sas prg/stsas/tab/programname2022Q1.sas DDMMMYYYY HH:MM

Subscale	Sov	Statistics	a	B	Product -	 م	 ਸ
Satisfaction	Male	n	Х	Х	Х	Х	Х
		n missing	Х	Х	Х	Х	Х
		Mean	X.X	X.X	X.X	X.X	X.X
		SD	X.XX	X.XX	X.XX	X.XX	X.XX
		CV (%)	XX.X	XX.X	XX.X	XX.X	XX.X
		SEM	X.XX	X.XX	X.XX	X.XX	X.XX
		Minimum	XX	XX	XX	XX	XX
		Q1	X.X	X.X	X.X	X.X	X.X
		Median	X.X	X.X	X.X	X.X	X.X
		Q3	X.X	X.X	X.X	X.X	X.X
		Maximum	XX	XX	XX	XX	XX
		95% CI	х.х-х.х	X.X-X.X	х.х-х.х	х.х-х.х	х.х-х.х

Table PESS Summary of PES Factor Scores Following Controlled Product Use by Sex and Product (Outcomes Population)

<Similar to above for all subscales and Sex = Female and Overall>

Programmer note: The table should include all the Subscales listed in Section 9.2.

Product A: < > Product B: < > Product C: < > Product D: < > Product E: < >

Source: ADaM.< > Program: /CAXXXX/sas\_prg/stsas/tab/programname2022Q1.sas DDMMMYYYY HH:MM

				Product -		
Sex	Statistics	A	В	С	D	E
Male	n	X	х	Х	х	Х
	n missing	Х	Х	Х	Х	Х
	Mean	X.X	X.X	X.X	X.X	X.X
	SD	X.XX	X.XX	X.XX	X.XX	X.XX
	CV (%)	XX.X	XX.X	XX.X	XX.X	XX.X
	SEM	X.XX	X.XX	X.XX	X.XX	X.XX
	Minimum	XX	XX	XX	XX	XX
	Q1	X.X	X.X	X.X	X.X	X.X
	Median	X.X	X.X	X.X	X.X	X.X
	Q3	X.X	X.X	X.X	X.X	X.X
	Maximum	XX	XX	XX	XX	XX
	95% CI	х.х-х.х	х.х-х.х	х.х-х.х	X.X-X.X	х.х-х.х

Table ITUS Summary of Intent to Use VAS Raw Scores Following Controlled Product Use by Sex and Product (Outcomes Population)

<Similar to above for Sex = Female and Overall>

Programmer note: Table 14.2.3.3.2 will resemble the shell above with bipolar scores.

Product A: < > Product B: < > Product C: < > Product D: < > Product E: < >

Source: ADaM.< > Program: /CAXXXX/sas\_prg/stsas/tab/programname2022Q1.sas DDMMMYYYY HH:MM

				Product -		

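### The Product Evaluation Scale and Intent to Use get no confidence interval for the within-subject difference from the subject's own cigarette; adding one is a cheap improvement

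*SAP*

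**What the plan says.** Objective 3 in SAP 2.1 reads "To evaluate product perception and preference using subjective assessments". Protocol 1.3 describes the purpose of the data in comparative terms: "nicotine PK, product perception and preference, product usage as measured by topography and tolerability and safety of each of the products compared with" the subject's own brand of cigarette.

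The planned analysis is descriptive in both documents:

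- **PES, SAP 9.2:** "Descriptive statistics of the subscales will be provided by study product, by sex and overall". Protocol 7.3.2.2 plans the same.
- **ITU, SAP 9.3:** "Descriptive statistics of the VAS raw score and bipolar score will be provided by study product", and "A frequency count table will be presented for the categories of the bipolar scores". Protocol 7.3.2.3 is equally descriptive: "Descriptive statistics of the VAS will be provided by study product".
- **Shells, SAP 15.2:** PESS ("Summary of PES Factor Scores Following Controlled Product Use by Sex and Product (Outcomes Population") and ITUS ("Summary of Intent to Use VAS Raw Scores Following Controlled Product Use by Sex and Product (Outcomes Population") have one column per product, each with n, mean, SD, CV, SEM, quartiles, range and a 95% CI. Neither has a difference column. The per-product CI appears only in the shells, not in the text of 9.2 or 9.3.
- **Table list, SAP 14:** one PES summary table, two ITU summary tables and one ITU frequency table. There is no statistical comparison table for either instrument.

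For Urge to Smoke (SAP 9.1) and puff topography (SAP 10), the same SAP fits the crossover model with sequence, period, product and subject within sequence. It reports differences in least-squares means (LSM) with 95% CIs and p-values for every pair of products.

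**The concern.** Each subject rates all five products, so the natural measure of perception relative to the cigarette is the difference within a subject. The planned tables show five separate columns. A reader who wants to know whether a heated product was rated better or worse than the own brand gets two means and two intervals, each containing between-subject spread, and no interval for the gap.

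The bipolar ITU score does not fill this role. It is the VAS score minus 50, so it expresses absolute intent to buy one product, not preference over the cigarette.

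At stake is how well the report can support a statement about satisfaction, reward, aversion, relief or purchase intent compared with own-brand cigarettes. SAP 1 treats analyses outside the plan as out of scope, to be described in the study report. A comparison made later would therefore not be pre-specified.

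**Working it through.** The plan states no power or precision figure to reproduce; SAP 4 says the sample size was chosen without statistical considerations.

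**Inputs from the documents.** 25 subjects, five sequences (ABECD, BCADE, CDBEA, DECAB, EADBC) with 5 subjects each (SAP 5); 95% intervals (SAP 8.6).

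**Assumed inputs.** The documents give no SD or within-subject correlation for PES or ITU. I take a common SD s and a correlation r between two products from −0.3 to 0.7.

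**Step 1: is the contrast estimable?** Each product occurs once in every period across the five sequences, so the design is a Latin square. With complete data there are 25 × 5 = 125 observations. The rank is 25 (subjects) + 4 (periods) + 4 (products) = 33, which leaves 92 residual df. The variance of a product-minus-E contrast is 2σ_w²/25 = 0.08σ_w², where σ_w² = s²(1 − r). Products are balanced over subjects and periods, so the difference of two column means equals the model's LSM difference.

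**Step 2: can the precision be read from the planned tables?** The variance of the difference of two column means is (s_A² + s_E² − 2·r·s_A·s_E)/25. The tables show s_A and s_E but not r, so it cannot.

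**Step 3: what difference does r make?** The half-widths of the 95% CI are:

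- Paired difference: t(24) × s × √(2(1 − r)/25), with t(24) = 2.064.
- SAP 8.6 model: the same expression with t(92).
- Pairing ignored: t × s × √(2/25) = 0.58s with t(24), or 0.57s with t(48).

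| r (assumed) | Paired, t(24) | Model, t(92) | Model relative to unpaired, t(48) |
|---|---|---|---|
| −0.3 | 0.67s | 0.64s | 1.13 |
| 0 | 0.58s | 0.56s | 0.99 |
| 0.3 | 0.49s | 0.47s | 0.83 |
| 0.5 | 0.41s | 0.40s | 0.70 |
| 0.7 | 0.32s | 0.31s | 0.54 |

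Worked line for r = 0.5: 2.064 × √(2 × 0.5/25) = 2.064 × 0.2 = 0.41.

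**Step 4: on the scales used, with assumed SDs.** For ITU at s = 30 mm, the model half-width is 14.1, 11.9 and 9.2 mm at r = 0.3, 0.5 and 0.7, against 17.1 mm unpaired. For PES at s = 1.5 points it is 0.70, 0.60 and 0.46, against 0.85.

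These are interval widths, not statements of power.

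**The case against.** The strongest reply is that the descriptive scope looks deliberate. The primary objective says 'evaluate and compare', while objective 3 says only 'evaluate'. Protocol 7.3.2.1 and 7.3.3 call for a statistical comparison of urge and topography parameters; 7.3.2.2 and 7.3.2.3 do not call for one for PES and ITU. The SAP follows the protocol. This stands, and it rules out calling the gap an inconsistency or an omission against plan.

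A reader might also infer that the pairing is thrown away and that the difference from the cigarette is never estimated. The documents do not support that. The listings in Appendices 16.2.6.7 to 16.2.6.9 keep every score by subject and product, and with complete data subtraction gives the point difference. Nor is the output limited to means: medians, quartiles and ITU category counts are planned too, though also separately by product.

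Part of the content is covered elsewhere. Urge to Smoke receives model-based differences from E, and PES items 11, 14 and 20 overlap with it. Satisfaction, psychological reward, aversion and purchase intent have no such counterpart.

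Finally, a precision gain is not assured. Own-brand ratings may correlate weakly or negatively with ratings of unfamiliar products, and SDs may be unequal if own-brand intent sits near the top of the scale. This stands. It limits the claim about size, but not the point that the summary tables leave the uncertainty of the difference unknown.

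**Conclusion.** A cheap improvement is available; nothing in the plan is wrong or contradictory. No CI is planned for the within-subject difference between any product and the own cigarette on PES or ITU, and the planned summary tables do not allow one to be derived. That conclusion needs no assumption about SD or correlation. After any dropout, summaries on reduced denominators (protocol 7.3) mean that the columns describe partly different subjects, so plain subtraction is no longer purely within-subject.

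The size is illustrative only. At assumed r of 0.3 to 0.7 the paired interval is clearly narrower than one that ignores pairing. At r = 0 there is no gain. At r = −0.3 the model interval is 1.13 times as wide, so ignoring pairing would be overconfident. A reader might go further and say that real differences will be missed because the five intervals overlap. The plan states no overlap rule, so that cannot be claimed.

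**What to change.** In SAP 9.2 and 9.3, apply the SAP 8.6 model (sequence, period and product fixed; subject within sequence random; no transformation) to the four PES subscales and the raw ITU VAS score. Report LSM differences with 95% CIs for A, B, C and D versus E, using shell SCUTS without its p-value column. State that the intervals are descriptive and unadjusted for multiplicity.

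If a non-parametric result is wanted, because scores may cluster at the scale ends, pre-specify the paired Hodges-Lehmann estimate and CI already described for Tmax. Make it a fixed sensitivity analysis, not a switch decided after seeing the data. It carries no period adjustment, which is one reason to keep it secondary.

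No new data are needed, and the code and shell exist. Protocol 7 allows additional analyses to be included in the SAP and ties a protocol amendment to major changes in the primary endpoints or their analysis, so none appears necessary. The cost is two more tables and 5 scores × 4 contrasts = 20 more unadjusted intervals. Dropping the p-values does not remove the multiplicity, since each interval can still be read as a 5% test; hence the label.
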